- Hypoxic or hypercarbic respiratory arrest

Secondary outcomes in the study will be:

1. Surgical Tolerability

- Measured by a designed instrument that will be completed by the surgeon and anesthesia staff and will include reporting of the following (See “Data Collection: Surgical Tolerability”)
 - Patient movement: Major (limb movement, coughing on ventilator), minor (diaphragm movement), none
 - Movement interfering with surgical progress: Yes, no
 - Surgical conditions: Excellent, good, poor
 - Total dose supplemental propofol required for suppression of movements
 - BIS recorded during patient movement

2. Weakness (See “Data Collection: Postoperative”)

- Blinded assessment of patient experience of weakness or respiratory difficulties on postoperative survey (See “Postoperative Survey”)

Study Risk and Benefits

When continuous muscle relaxation is omitted, there is a risk of movement under anesthesia (e.g. coughing, limb muscle movement), which may interfere with surgery. Movement under anesthesia occurs occasionally even when muscle relaxation is provided continuously (during standard of care), but in the absence of muscle relaxation (non-standard of care), these movements may be more pronounced. Other anesthesia medications (i.e. anesthetic agents,

analgesic agents) are provided when muscle relaxation is not being administered to minimize these risks. In our study, midazolam and fentanyl (standard of care medications) will be administered in doses to avoid the potential for inadvertent movement. In the low dose muscle relaxant group, inadvertent patient movement will be treated with additional anesthesia with propofol, increasing the dose of volatile anesthetic, administering pain medication or if necessary for patient safety, administering muscle relaxants as required (i.e. reverting to standard of care). The risk of movement under anesthesia when low dose muscle relaxant is used is reasonable because providing anesthesia without muscle relaxation is an established technique used for other types of surgery (e.g. non cardiac).

As muscle relaxation has been associated with harmful effects (e.g. postoperative pulmonary complications), the use of low doses has some potential benefit. Results from this study may help future patients having cardiac surgery by providing guidance to the best way to conduct anesthesia to minimize respiratory complications.

Monitoring of Safety

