There will be ongoing (case by case) review of adverse events and safety information between the principal investigator and co-investigators and any events will be addressed. Unanticipated problems requiring a revision to the protocol will be submitted to the IRB for review. A Data Safety Monitoring Board has been convened and will review the results early in the study as well as halfway through enrolment to address any safety concerns. A continuing review with examination of preliminary data will be conducted after 50 patients have been recruited.

Unanticipated problems (i.e. unexpected events that are related or possibly related to participation in the research that suggest that the research places subjects or others at risk of unknown harm or increased frequency of harm) will be reported to the IRB within 10 working

days of the investigator's knowledge of the event. In the event of a fatal or life-threatening unanticipated problem, enrolment will be halted and the IRB chair notified by phone immediately. A major deviation from the protocol will be reported within 10 working days via the "Unanticipated Problem" form. A minor deviation will be summarized at the time of continuing review on the "Continuing Review Form".

Power Calculation:

Previous studies of respiratory complications after cardiac surgery have suggested incidence rates ranging from 0.5-30%.^{26,27,33-35} Many of these studies include atelectasis and pleural effusions in their composite calculation of respiratory complications, which are problematic because of diagnostic difficulty and less clear relationship to NMB use. The current study will focus solely on the respiratory complications previously defined. Assuming this composite has a potential incidence of 20% and that the effect size is 0.5, a total of 47 patients will be required in each arm to achieve a power of 80% with a $p=0.05$. A total of 100 patients will be recruited to account for crossover.

Inclusion Criteria

All patients >18 years old undergoing elective cardiac surgery (coronary artery bypass grafting [CABG], valve replacement or CABG + valve replacement) requiring cardiopulmonary bypass at the University of Chicago with one of two surgeons ([name] or [name]).

Exclusion criteria

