Emergency surgery, extremes of age (<18 or >90 years), previous cardiac surgery, clinical contraindications to succinylcholine or cisatracurium, anticipated difficult tracheal intubation, preoperative mechanical ventilation, preoperative pharmacologic/mechanical hemodynamic support.

Study Protocol

Institutional Review Board approval will be obtained and the study will be registered with www.clinicaltrials.gov prior to commencement. All patients enrolled in the study will be randomized to either a standard protocol (Group CIS) or the single-dose NMB protocol (Group SUX) (See “Intraoperative Protocol”). All study and anesthetic drugs will be administered by the anesthesia care team. The neuromuscular blocking agents being studied will be dispensed by the operating room pharmacy, as is routine, and drawn up in the operating room for intravenous administration. ICU providers and surgeons will be blinded to the study group assignment, and intraoperative and postoperative care will otherwise be routine.

No compensation will be provided to study participants. Patients will be identified by review of operative room schedules and consent will occur prior to the standard preoperative interview. The data set created from study information will be maintained following study completion but all patient identifiers will be deleted. This will be maintained for a minimum of 6 years. Consent forms with patient identifying information will be held in a locked file in a locked office for a minimum of 6 years. Randomization will be performed by computer generation. Data analysis will be performed on an intention to treat basis.

Data Collection

The investigators will collect the following data points.

Patient Factors – See “Data Collection: Preoperative”

Intra-operative Factors – See “Data Collection: Intraoperative and Data Collection: Surgical Tolerability”

Post-operative factors – See “Data Collection: Postoperative, Data Collection: Respiratory Complications, Data Collection: Postoperative Survey”

Intraoperative Protocol

Patients are to receive the same standardized doses of medications as a total for the case. Induction/maintenance medications are to be administered with induction or prior to CPB, as hemodynamics allow. IV boluses of phenylephrine (100mcg), vasopressin (1 unit), ephedrine (10mg) or norepinephrine (8mcg) may be administered as required.

Induction/maintenance:

- Midazolam 0.1mg/kg
- Fentanyl 15 mcg/kg

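### The 47 per arm does not follow from the stated inputs: a two-sided halving from 20% to 10% needs 199 per arm and has about 27-29% power, and the effect scale, sidedness and test are undefined

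*Combined protocol and SAP*

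**What the plan says.** The primary outcome is binary: any listed respiratory complication in the 72 hours after ICU admission (Methods). The whole sample size justification is in the Power Calculation section. It takes an "incidence of 20% and that the effect size is 0.5, a total of 47 patients will be required in each arm", for 80% power with p=0.05. It then adds: "A total of 100 patients will be recruited to account for crossover". The same section cites earlier studies with respiratory complication rates between 0.5% and 30%.

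Two other statements bear on the calculation. Study Risk and Benefits lets patients in the low-dose group who move receive further treatment, including, where safety requires it, "administering muscle relaxants as required (i.e. reverting to standard of care". Study Protocol says "Data analysis will be performed on an intention to treat basis". No statistical test, sidedness or expected rate in the second arm is given anywhere.

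**The concern.** A sample size for two proportions needs two rates, or one rate and an effect on a named scale. Here there is one rate, not assigned to an arm, and the statement that "the effect size is 0.5", which could be a relative risk, an odds ratio, a standardised difference or an absolute difference. A reader cannot verify 47 from that. It also looks far too small for the kind of reduction the trial seems to be about: at 50 per arm, 20% versus 10% means about 10 events against 5.

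The interpretation of the primary result is at stake. A plan with 80% power claims a 20% chance of missing its target effect. If the true chance is about 70%, a non-significant result says little about whether avoiding continuous neuromuscular blockade lowers respiratory complications, yet the stated power invites the opposite conclusion.

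**Working it through.** **Inputs from the plan:** incidence 0.20; effect 0.5, scale not given; power 0.80; alpha 0.05, sidedness not given; 47 per arm, 94 in total; 100 recruited, so 50 per arm if allocation is equal.

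**Formulas (normal approximation, equal arms).** With d = |p1 − p2| and p̄ = (p1 + p2)/2:

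- n per arm = [z_α √(2p̄(1−p̄)) + z_β √(p1(1−p1) + p2(1−p2))]² / d²
- power = Φ{[d√n − z_α √(2p̄(1−p̄))] / √(p1(1−p1) + p2(1−p2))}
- standardised effect h: n per arm = 2(z_α + z_β)² / h²

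Here z_β = 0.842, and z_α = 1.960 two-sided or 1.645 one-sided.

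**Attempt to reproduce 47, starting with 20% versus 10%.** p̄ = 0.15, √0.255 = 0.505 and √0.25 = 0.5.

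- Two-sided: (1.960 × 0.505 + 0.842 × 0.5)² / 0.01 = 198.96, so 199.
- One-sided: 156.6, so 157.
- Two-sided power at 47: Φ[(0.6856 − 0.9897)/0.5] = Φ(−0.608) = 0.271.
- Two-sided power at 50: Φ[(0.7071 − 0.9897)/0.5] = Φ(−0.565) = 0.286.

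**Other readings of 0.5:**

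| Reading | n per arm, two-sided | n per arm, one-sided | Two-sided power at 47 / 50 |
|---|---|---|---|
| Relative risk 0.5: 20% vs 10% | 199 | 157 | 27% / 29% |
| Odds ratio 0.5: 20% vs 11.1% | 260 | 205 | 22% / 23% |
| Halving, 20% the average of both arms: 26.7% vs 13.3% | 141 | 111 | 36% / 38% |
| Halving, 20% the lower rate: 40% vs 20% | 82 | 64 | 56% / 59% |
| Standardised 0.5 (Cohen's h) | 63 | 50 | 68% / 71% |
| The same as rates, 20% vs 4.5%, pooled test | 69 | 55 | 63% / 66% |

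One-sided power at 47 / 50 is 39% / 40% for 20% versus 10%, and 78% / 80% for the standardised 0.5.

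**Figures closest to 47.** 20% versus 50%, two-sided with continuity correction, gives 45 (39 without it). 20% versus 42.8%, one-sided and unpooled, gives 48. Both put one arm above the 30% ceiling of the plan's own cited range, and neither is stated.

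**What 47 would require.** For a two-sided halving to need only 47 per arm, the control rate would have to be about 56%. At the top of the cited range, 30% versus 15% still needs 121 per arm and has 41% / 43% power at 47 / 50.

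**What 50 per arm can detect.** Starting from 20%, two-sided 80% power by the normal approximation needs a fall to about 2.5% (2.1% at 47 per arm).

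**Dependence on the test.** With Fisher's exact test, two-sided power for 20% versus 10% is 17.6% at 47 and 19.5% at 50. For 20% versus 2.5% at 50 per arm, Fisher gives 73%, and it needs a rate between 1.5% and 2% to reach 80%.

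**Crossover.** The plan gives no rate, so these figures are illustrations for 20% versus 10%, two-sided, 50 per arm.

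- If patients who revert take on the full control risk (assumed), reversion of 0%, 5% and 10% gives experimental-arm rates of 10%, 10.5% and 11%, with power 29%, 26% and 24%.
- If they take on half the excess risk (assumed), 10% reversion gives 10.5% and 26% power.
- Going from 94 to 100 offsets a crossover fraction of 1 − √(94/100) = 0.030, about 3%, under the first assumption and about 6% under the second.

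**The case against.** The strongest reply is that the plan never says halving. It says only that the effect size is 0.5, and in some software that phrase means a standardised difference. On that reading with a one-sided test, 50 per arm are needed, power is 78.2% at 47, and the 50 per arm actually recruited give 80.4%. The shortfall would then be slight. It follows that the 27-29% figure is conditional on a two-sided halving, and it is presented that way here.

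The reply does not rescue the paragraph. It still gives 50 rather than 47, it makes no use of the 20% the plan supplies, and no one-sided test is stated. Two-sided, the same reading gives only 68-71%. Written as rates starting from 20%, it means a fall to about 4.5%, which needs 55 per arm even one-sided with the pooled test.

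Two smaller objections also stand in part. The detectable rate of about 2.5% depends on the test and must be labelled as a normal approximation. Crossover is secondary: under the rates assumed above it moves power only from 29% to 24%, and the plan already fixes intention to treat as the analysis.

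**Conclusion.** The concern holds. Without choosing any reading, two things are established: the effect scale, second-arm rate, sidedness and test are missing, and none of the readings tried gives 47 from the stated inputs except by implying a rate above the plan's cited range.

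The size of the gap depends on the intended effect. For a two-sided halving from 20%, the stated number is short by a factor of about four (199/47 = 4.2). The chance of missing the effect is then 71-73% instead of 20%. It is 60-61% for a one-sided halving and 29-32% for a two-sided standardised 0.5. These figures rest on equal allocation and the normal approximation, before any crossover; Fisher's test lowers the power for a halving further. The plan does not show that six extra patients offset the dilution from reversion under intention to treat.

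**What to change.** N=100 can stay; the paragraph has to be corrected.

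1. State the intended effect as two event rates, or on a clearly defined scale, with the sidedness and the test.
2. Replace the 80% claim with the power that 50 per arm gives for that effect under the named test, and add the difference detectable at 80% power. If the target is 20% versus 10%, two-sided, the normal approximation gives about 29%, with a detectable fall from 20% to about 2.5%. Under Fisher's test the figures are 19.5% and a rate between 1.5% and 2%.
3. Replace the crossover remark with intention-to-treat power at stated crossover rates, for example 0%, 5% and 10%, and state the risk assumed for patients who revert.
4. Report the primary result with a 95% confidence interval.

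The cost is protocol wording only, with no extra patients. The drawback is a less favourable stated power. The sponsor could instead change the sample size or the target effect, but steps 1 to 4 would still be needed.
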